## 1.0 Study Summary

Study Title	The impact of sharing audio recorded clinic visits on self-management in older adults: a multi-site trial
Study Design	Multi-site, patient level, randomized controlled trial. The three sites are Dartmouth-Hitchcock Primary Care (D- H; Manchester, NH and Bedford, NH), Vanderbilt University Medical Center (VUMC; Nashville, TN), and University of Texas Medical Branch, (UTMB; Galveston, TX).
Primary Objective	To determine the feasibility of a multisite trial of audio-recording
Secondary Objective(s)	Gather preliminary data on impact on behavioral, health and health care utilization outcomes.
Research Intervention(s)/ Investigational Agent(s)	Audio-recording of clinic visit shared via HIPAA compliant website.
IND/IDE #	N/A
Study Population	Older adults ( $\geq 65$ years) with diabetes mellitus (Type 1 or 2) and hypertension managed in an outpatient setting.
Sample Size	Aim 1: N=108 (30 patients and 6 clinicians per site) Aim 2: N=54 (6 trial patient-participants and 6 trial clinician-participants from each site total N=18 patients, N=18 clinicians and 6 caregivers of trial patient participants per site, total N=18-caregivers). In addition to this, we will plan to supplement our interviews with two additional Spanish language patient and caregiver participants at our UTMB site if participants wish to take part.
Study Duration for individual participants	3-4 months
Study Specific Abbreviations/ Definitions	

PROTOCOL TITLE: *The impact of sharing audio recorded clinic visits on self-management in older adults: a multisite trial*

## 2.0 Objectives\*

**Aim 1. Conduct a multi-site, two-arm, parallel group, patient-randomized, blocked, controlled, pilot trial with 3-month follow up, to determine the feasibility and acceptability of sharing audio recordings of clinic visits (AUDIO) on self-management in older adults with diabetes and hypertension, compared to the after visit written summary (AVS) alone (Usual Care/UC).** We will determine:

- 1.1 *Feasibility* of a larger trial by meeting recruitment targets at each site (n=30 patients and 6 clinicians per site; total N=108) and determining the optimal strategy to achieve a high retention rate and adherence to the study protocol.
- 1.2 *Acceptability* by assessing the proportion of patients and clinicians who agree to take part in the project and the proportion of patients who listen to the recording.
- 1.3 *Potential effectiveness* by collecting data on the impact of audio recordings on patient experience, understanding, self-management and clinician behavior. *We will explore our main hypothesis that compared to those receiving UC, patients randomized to also receive audio recordings (AUDIO) of clinic visits will report greater self-management (Patient Activation Measure – Short Form) at 3 months. We will also explore whether the effect of AUDIO on self- management compared to UC is greater for patients with low health literacy than those with high health literacy.*

**Aim 2. Assess the acceptability of study protocol and the use of audio recording of visits as part of care** by conducting semi-structured interviews with participating clinicians, patients and caregivers (i.e. person involved in the patient's care, including a family member, friend or formal caregiver).

We hypothesize that this multisite trial will be highly feasible and that recording and sharing of clinic visits will be highly acceptable.

## 3.0 Background\*

### 3.1. Significance

Up to 80% of healthcare information is forgotten by patients *immediately* following a clinic visit. Poor recall of medical information has been identified as a significant barrier to self-management, key to the Chronic Care Model. This barrier is amplified in older adults with multimorbidity, where reduced cognitive capacity, low health literacy, and complex treatment plans are common. Older adults with multimorbidity account for 96% of Medicare expenditures, and in the absence of optimal self-management, they experience low quality of life and functional decline. Yet,

PROTOCOL TITLE: *The impact of sharing audio recorded clinic visits on self-management in older adults: a multisite trial*

when these patients are “activated,” they recognize that they have an important role in self-managing their conditions and have the knowledge, skills, and confidence to do so resulting in better functional status and health outcomes.

A written after-visit summary (AVS) is the current U.S. standard of addressing poor recall of visit information with the goal of improving patient’s ability to self-manage. The AVS includes information on diagnoses, medications, allergies, clinician visited, and visit summary recommendations. While access to visit information is highly valued by patients, several factors limit the usefulness of the AVS, such as the layout of information and the accuracy of the summary, resulting in confusion in patients and low AVS use.

Audio recording of visits is a novel alternative that, in contrast to the standard AVS, provides a full detailed account of the clinic visit. Evidence suggests that sharing recordings can lead to greater patient recall and understanding of visit information and is acceptable to clinicians and patients. In our national survey (456 clinicians and 524 patients), 28% of clinicians reported having recorded a clinic visit for a patient’s personal use at least once, while 18% of patients had recorded a visit for their own use at least once. Clinics are becoming aware of the potential of sharing recordings of visits and some offer this to their patients.

Despite their emerging use in clinical practice, we do not know the impact—positive or negative—of audio recordings on patients’ self-management or other health-related outcomes: especially relevant to older patients with chronic disease where self-management is critical. To answer this question, we propose a multi-site pilot trial of older adults with diabetes and hypertension in preparation for a fully powered trial to evaluate the impact of augmenting the AVS with audio recordings of the clinic visit compared to the AVS alone (Usual Care; UC).

Consistent with *PA-18-376 Self-Management for Health in Chronic Conditions*, and aligned with *NIA Strategic Goal C*, our long-term goal is to improve patient health outcomes through better self-management. Our objective in the proposed project is to: (a) operationalize and determine the feasibility of a multi-site trial where clinic visits are audio recorded and shared with older adults with diabetes and hypertension; (b) gather preliminary data examining the impact of routinely adding audio recordings of clinic visits to UC on self-management ability; and (c) identify factors pertinent to the acceptability of our study protocol and the audio recording of visits. Hypotheses are based on our substantial preliminary work and supporting evidence from scoping and systematic reviews.

PROTOCOL TITLE: *The impact of sharing audio recorded clinic visits on self-management in older adults: a multisite trial*

### **3.2 Preliminary Data**

Our research team has conducted substantial preliminary work in this area, highlighting the acceptability of recording, feasibility of our trial and scalability of recording in practice. We describe this work below.

**3.2.1 The prevalence of clinic audio recording in the U.S.** Our research group (MPIs [name], [name] and [name]) conducted a cross-sectional survey of 456 U.S. based clinicians, using SERMO clinician panels, and 524 members of the U.S. public, using Qualtrics Panels with quotas based on U.S. census data for age, sex, education, language spoken at home, race and ethnicity. As described above, a significant proportion of clinicians and the public have recorded or are willing to record clinic visits (see Section 3.6).

**3.2.2 The routine sharing of audio recordings in America: a case study of clinics.** Drs. [name] and [name] conducted a case study at three clinics that routinely share visit recordings: the Ryan Family Practice (Ludington, MI); the Barrow Neurosurgical Institute (BNI) (Phoenix, AZ); and the University of Texas Medical Branch (UTMB) Cancer Center (League City, TX). Seventy interviews were conducted with patients, caregivers, clinicians and administrators to understand implementation strategies, motivations, and recording use. Of the 34 patients and caregivers interviewed, 17 (50%) were  $\geq 65$  years, 28 (82%) reported listening to and 16 (47%) shared recordings. Major themes include the benefits of recording on patient understanding and recall, patient use of recordings to prepare for visits and greater engagement of caregivers. At BNI, clinicians who record now receive a 10% reduction in malpractice premiums and a \$1 million increase in liability.

**3.2.3 “Taking the Message and the Medicine Home” program, UTMB, Galveston, TX.** [name] led and coordinated the implementation of routine recording at UTMB beginning in 2010 with oncology outpatient clinics and breast health clinics. All patients in their first visit to the clinic are informed about recording and are offered a digital recorder. In 2017, a diagnosis code was added to the Epic EMR system to indicate when a patient records during the encounter. The system reports, in 2017, 1,100 unique patients' recordings.

**3.2.4 Are patients allowed to audio record medical visits?** The emergence of audio recording in clinic practice has raised questions about its legality. We published in *JAMA* an analysis of legal statutes related to recording. Our analysis finds that patients recording clinic visits do not require clinician consent in 39 states and the District of Columbia (single party consent; including TN and TX), but they do require

PROTOCOL TITLE: *The impact of sharing audio recorded clinic visits on self-management in older adults: a multisite trial*

consent in 11 states (all party consent; including NH). Health Insurance Portability and Accountability Act (HIPAA) regulations only applied to recordings that are owned by a health entity, not those that are owned by a patient.

**3.2.5 Heart Sounds Pilot Trial.** In collaboration with [name] and Dartmouth CTSA support, [name] is currently leading a pilot trial to determine the acceptability and feasibility of sharing audio recordings of inpatient discharge instructions, compared to a written discharge summary (usual care), with cardiology inpatients (mean age: 67 years). This study mirrors the methods of the current proposal, including the approach to randomization, recruitment strategy, data collection procedures – however patients received a digital recorder. All eligible providers consented to take part in the project (N=6). We recruited 57 participants in 5 months (a recruitment rate of 56%) with an attrition rate of approximately 30%. The study protocol was administered with high fidelity.

**3.2.6 Patient-Provider Communication in Patients with Diabetes and Depressive Symptoms.** [name] led a project that included the audio recording of 95 primary care visits of adults with diabetes, evaluating the association between depressive symptoms and patient-centered communication. Similar recruitment methods were used as in the current project. No primary care clinicians refused to participate. Procedures were developed to ensure integration into clinical practice workflow, including privacy protection of people in the clinic but not involved in the research study, and these will be applied in the current proposal.

**3.2.7 Developing an audio personal health library (Audio PHL) for older adults with multimorbidity.** We have developed an application that supports the recording of clinic visits, performs secure transfers of these recordings to a HIPAA-compliant server infrastructure at Dartmouth, and allows patient-participants to set up a password-protected account to listen, share and manage their recordings online ([name], GBMF#4952, STUDY00030397, STUDY00030126; [name], R01LM012815; STUDY00030531). This system will be used in the current project.

**3.2.8 Piloting of patient identification, recording strategies and data collection instruments.** In preparation for this study, EMR reports were generated to estimate the number of patients meeting the study criteria on a weekly basis at each study site, demonstrating the feasibility of generating this report and confirming the pool of potential patients for our trial. All sites have experience in recording of clinic visits as described above. Across our study sites we conducted ten feedback sessions with clinical staff, leadership, and patients to guide study design and selection of recording device. We also piloted the proposed assessments with older adults (≥65 years).

PROTOCOL TITLE: *The impact of sharing audio recorded clinic visits on self-management in older adults: a multisite trial*

Baseline assessment took approximately 20 minutes (n=12), provision of recording instructions took 10 minutes and follow up assessments by telephone (n=10) took 20 minutes.

## 4.0 Study Endpoints\*

### 4.1 Primary endpoint

The primary endpoints of this pilot trial are:

1) Feasibility: We will determine the optimal strategy to achieve a high retention rate and adherence to the study protocol. We will also assess retention rates (proportion of included patients completing T2 follow up; we will target >70%), fidelity to the study protocol (Borrelli et al criteria; we will target >90%) and the Feasibility of Intervention Measure (FIM, 4 items, see Appendix 1. 3-month Follow Up Assessment (T2); we will target an average score of >3).

2) Acceptability: We will determine the acceptability of the AUDIO intervention and study protocol by assessing the proportion of patients and clinicians who agree to take part in the project and proportion of patients who listen to the recording. Our primary indicator of acceptability will be the recruitment of 108 participants (N=30 patients and 6 clinicians per site) over our planned data collection period of six months. We will determine the listening rates (we will target >70%): this will include the proportion of patients in the intervention arm that log in to the online system and listen to (and how often) the recording. We will also document the number of patients who share or report sharing the recording and caregivers who access the recording. Participants will complete the Acceptability of Intervention Measure (AIM, 4 items, see Appendix 1. 3-month Follow Up Assessment (T2); target an average score of >3).

### 4.2 Exploratory endpoints

We will also gather data on exploratory endpoints. These are outlined in Table 1.

**Table 1.** Exploratory outcome measures and timing of data collection

Measure	Description	Standard assessments*			Corresponding Appendix
		T0	T1	T2	
Exploratory outcomes					

PROTOCOL TITLE: *The impact of sharing audio recorded clinic visits on self-management in older adults: a multisite trial*

Patient Satisfaction Questionnaire-18  M (S) 	18-item PROM of patient satisfaction with care, with seven domains.	X	X	X	Appendix 2
PAM-SF  (S) 	13-item PROM. Four domains: Patient: i) recognizes their role; ii) has knowledge and confidence; iii) takes steps to manage care; and iv) can manage care under stress	X	X	X	Appendix 2
Medical Outcomes Study General Adherence measure  (S) 	Five-item PROM of patient adherence to treatment.	X		X	Appendix 2
Adherence to Refills and Medications (ARMS- 7)	Seven-item PROM of medication adherence.	X	X	X	Appendix 2
Global PROMIS  & EURO-QOL  (S) 	10-item PROM of mental and physical health. Scores can be converted to EURO-QOL scores.	X	X	X	Appendix 2
Patient Health Questionnaire (PHQ-8)	Eight-item PROM of depression	X		X	Appendix 2
Generalized Anxiety Disorder (GAD-7)	Seven-item PROM of anxiety	X		X	Appendix 2
Comprehensive Diabetes Stigma Scale (CDSS-15)	15-Item PROM of diabetes-related stigma	X		X	Appendix 2
Stigma Scale for Chronic Illness (SSCI-8)	Eight-item PROM of stigma related to chronic illness	X		X	Appendix 2
ER visits & hospitalization	ER visits and hospitalizations abstracted from the EHR during the study period.			X	

PROTOCOL TITLE: *The impact of sharing audio recorded clinic visits on self-management in older adults: a multisite trial*

Health services utilization	Health services utilization including primary care contacts (e.g., phone calls and visits) and visits to specialists (e.g., endocrinology, nephrology and ophthalmology), abstracted from the EHR during the study period.		X	
Quality of diabetes care	Proportion of patients receiving guideline-concordant care in line with Standards of Medical Care in Diabetes (e.g., A1c, urine albumin, referral for retinal exam, and in those with HbA 1c > 8% we will collect data regarding intensification of medication therapy)	X	X	
Quality of hypertension care	Proportion of patients receiving guideline-concordant care in line with Standards of Medical Care in Hypertension		X	
	T0 (Baseline Assessment; pre-visit); T1 (1 week); T2 (3 months); from enrollment; PAM-SF (Patient Activation Measure Short Form); Global Patient-Reported Outcome Measurement Information System ( PROMIS ); QOL (Quality of life); ER (Emergency Room). ( S ) Spanish language; PROM (Patient Reported Outcome Measure). Note: the Interpersonal Process of care (IPC) survey will be administered after T0 in clinic (or at T1 if not yet completed) AND within 7 days of interim scheduled clinic visits (Tx) during the data collection period.			

PROTOCOL TITLE: *The impact of sharing audio recorded clinic visits on self-management in older adults: a multisite trial*

## 5.0 Study Intervention/Investigational Agent

**5.1 Usual care (UC):** During the trial, patients will receive the AVS per the current standard at each site. The AVS is similar at all sites, as each clinic uses EPIC, and includes information such as clinician comments, diagnoses, orders and results. It is available both in paper and via the patient portal

**5.2 Audio Intervention:** We will audio record both in-person and telehealth visits of patients in the intervention group. For in-person visits, the RA will follow standardized instructions demonstrating how to start and stop the recording on the electronic tablet with patients and ask patients to demonstrate to confirm understanding. The RA will then enter the exam room and begin the recording with the patient's permission, after the medical assistant has completed rooming the patient and before the clinician enters. The patient and clinician can choose to stop or start the recording at any time and a sign on the door will indicate "Recording in Progress". The RA will wait outside the visit room. Once the visit is complete, the RA will enter the room, turn off the recording, and bring the patient to a private room where the RA will follow standardized instructions demonstrating how to access recordings.

Telehealth visits may be recorded in two ways. 1) the RA will meet the clinician in the private room where the visit will take place, and follow standardized instructions demonstrating how to start and stop the recording on the electronic tablet with the clinician and ask the clinician to demonstrate to confirm understanding. The RA will then begin the recording with the patient's permission. A sign on the door will indicate "Recording in Progress". The RA will wait outside the visit room. Once the visit is complete, the RA will enter the room and turn off the recording. 2) The RA will receive a link to the telehealth visit. They will join the visit at the time it is due to begin. The RA will inform the patient and clinician that the visit will be recorded and will notify them once the recording has begun. The recording will be captured directly in to HealthPAL and a digital back up will also be used.

In both instances the patient and clinician can choose to stop or start the recording at any time by indicating this to the RA or stopping the recording device directly (e.g. where RA is outside of the room). The RA will schedule a time to meet with the patient via web conference, by phone or in person separate from the clinic visit, during which the RA will follow standardized instructions demonstrating how to access recordings. Pre- and post-visit surveys will be administered remotely, by email or telephone, for patients having telehealth visits.

The research team will maintain a copy of all recordings locally on a secure, HIPAA

PROTOCOL TITLE: *The impact of sharing audio recorded clinic visits on self-management in older adults: a multisite trial*

compliant server, captured by a second recorder, which will also serve as a back-up; once transferred to the server, the recording will be deleted from the digital recorder. Patient **access to recordings** will be possible via a secure web-based platform: HealthPAL.

HealthPAL. All patients with access to email will be able to access their recording online. The recording and sharing of the recorded data will be facilitated via HealthPAL, an online platform developed by PI [name] at Dartmouth (Appendix 4. HealthPAL system). The RA will register the patient in the HealthPAL system. Within the system they can record visits, which can then be accessed later online at home. The RA will demonstrate how to access and playback the recording on a computer or smartphone using each patient's unique login information. Access details (web address, login and use instructions) will be shared with patients both by email and on paper.

HealthPAL is a web application that runs on Amazon's cloud infrastructure (AWS). The root account under which the application is hosted is owned by Dartmouth College, which has a Business Associates Agreement (available upon request) in place with Amazon for the use of Amazon's HIPAA-eligible cloud services with Protected Health Information. All cloud services used by HealthPAL are covered under this agreement (Appendix. 5 HealthPAL security document).

**5.1.1 Listening regime:** We will instruct patients to listen to their most recent recording both within 24 hours after their visit (as a means to reinforce and recall self-management information discussed), at one week (to reinforce learning) and within three days prior to their next visit (to identify information that needs clarification orgaols of care they would like to raise with their clinician). A reminder to listen to the recording will be sent to patients by email and/or text message (Appendix 24. Patient HealthPAL Reminder Emails). Patients will have the option of providing the contact information (email) of a family member, or caregiver who typically assists, or is involved in their care, and the study team will send this person access to the recording via the website.

**5.1.2 Recording future visits:** The RA will review the EMR of participants and document in REDCap scheduled patient visits (up to 6 months from recruitment). For patients in the AUDIO group, the RA will also attend each visit and assist with recording as described above, and administer the IPC survey post visit. While patients in the UC group have no further in clinic procedures following baseline assessment, we will plan to attend these visits when possible and offer participants the opportunity to complete the IPC survey post visit. We anticipate that patients will have one additional scheduled clinic visit over the 3-month period based on the average number of visits of these types of patients estimated from EMR data at each clinic site in 2017. We will neither record nor conduct follow-up assessments of unscheduled/urgent or acute visits so as to

PROTOCOL TITLE: *The impact of sharing audio recorded clinic visits on self-management in older adults: a multisite trial*  
minimize burden on both participants and study staff.

**5.3 Device Handling.** An electronic tablet will be used to record clinic visits. By using the recording platform developed by PI [name], the actual recording will be automatically transferred to the cloud and not stored locally on the electronic tablet, reducing the risk of data loss in the unlikely event the electronic tablet is lost. The electronic tablet will be maintained by the research staff, before and after clinic visits. It will be password enabled and will be clearly marked as property of the study team. When not being used to capture recordings in the clinic, the electronic tablet will be stored securely in the office of the research coordinator at each site.

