Patients randomized to the AUDIO group will have their visit recorded using an electronic tablet; a second study recorder will also be used and act as a backup in case the primary recorder fails. For participants in the AUDIO arm, a sign will be placed on the clinic room door by the RA alerting others that a recording is taking place (see Appendix 6. Recording Sign). Upon completing their visit the RA will demonstrate to patients how to access their recording (see Appendix 7. HealthPal Instructions), and administer the post-visit baseline assessment survey items, specifically the PHQ-8 and GAD-7 surveys, and the Interpersonal Processes of Care Survey (IPC). These tasks may take place in clinic for patients having an in-person visit, or remotely by web conference, telephone, and/or email, for patients having a telehealth visit. Patients will identify times and days that are most convenient for follow up assessments, as well as contact information of a person who could be reached in the event they are unreachable. Patients will receive honorariums to promote retention; a thank you note will be mailed with \$30 (gift card, egift card, or site-specific payment method such as Greenphire) following recruitment and \$20 ( gift card, egift card, or site- specific payment method such as Greenphire) upon completion of each follow-up assessment.

**6.2 Monitoring, tracking, and retention:** RAs will receive standardized training on how

PROTOCOL TITLE: *The impact of sharing audio recorded clinic visits on self-management in older adults: a multisite trial*

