**Health literacy:** We will use two assessments, the 3-item validated Brief Health Literacy Scale (BHLS) and the 18-item validated Short Assessment of Health Literacy (SAHL-E). Both scales are validated in English and Spanish. Scores on the BHLS range between 3 and 15, with higher scores indicating higher subjective health literacy. Scores on the SAHL-E range from 0 – 18; ≤14 is considered low health literacy

**Disease burden:** The Charlson Comorbidity Index (CCI) using EMR data. Each condition is assigned a score, based on risk of death, which is summed, with higher scores indicating higher disease burden.

PROTOCOL TITLE: *The impact of sharing audio recorded clinic visits on self-management in older adults: a multisite trial*

**Depression:** The eight-item PHQ-8 validated in both English and Spanish. Scores range from 0 – 24; a score  $\geq 10$  indicates major depression, and a score of  $\geq 20$  indicates severe major depression.

**Anxiety:** The seven-item GAD-7 validated in both English and Spanish. Scores of 5, 10, and 15 represent cut points for mild, moderate, and severe anxiety, respectively.

**Diabetes Stigma:** The comprehensive diabetes stigma scale (CSSS-15) is a validated 15-item assessment of diabetes-related stigma. It is composed of four subscales: (1) enacted (0-6), (2) perceived (1-5) and (3) self-stigma(1-5), and (4) concealment (1-5). Subscale scores are means of responses, and an overall score is the sum of all items (11-96).

**Stigma of Chronic Illness.** The Stigma Scale for Chronic Illness (SSCI-8) is validated, eight-item assessment of stigma related to chronic disease. It is scored from 8 (low stigma) to 40 (high stigma), and can be converted on to a standardized T-distribution score with a mean of 50 and standard deviation of 10.

**Audio & AVS Use:** Intervention use by patients will be monitored within the HealthPAL application: we can determine when a 1. patient logs into their account; 2. listens to a recording; and 3. shares the recording. AVS use will be assessed at standard outcomes assessments and one week from scheduled clinic visit during the data collection period: we will determine whether the patient reviewed the AVS and whether they shared it.

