### **10.2 Inclusion / Exclusion Criteria (Aim 2 Debrief Interviews)**

#### **10.2.1 Inclusion/Exclusion Criteria (Aim 2)**

*Patients:* We will recruit a purposive sample of patient-participants from Aim 1 based on recording use (listened to none, one or all recordings; shared recording or not) and health literacy [SAHL-E score  $\leq 14$  (low health literacy) or  $> 14$  (high health literacy)].

PROTOCOL TITLE: *The impact of sharing audio recorded clinic visits on self-management in older adults: a multisite trial*

**Caregivers:** Patients will identify family members / caregivers who are 1)  $\geq 18$  years of age, 2) who can communicate in English or Spanish; and 3) have received access to the patient's audio recordings.

**Clinic staff:** We will include healthcare professionals and administrators who have been involved in the trial at each site including MDs, NPs, Nursing Staff, Medical Assistants, and Administrators.

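### The listening rate has no rule excluding the training session, where the RA demonstrates playback under the patient's own HealthPAL login, so it can be biased upward

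*Combined protocol and SAP*

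**What the plan says.** All references are to the combined protocol and SAP.

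- **Demonstration.** Section 5.2 (HealthPAL) states: "The RA will demonstrate how to access and playback the recording on a computer or smartphone using each patient's unique login information". Section 6.0 places this after the visit: "Upon completing their visit the RA will demonstrate to patients how to access their recording". For telehealth visits, section 5.2 says: "The RA will schedule a time to meet with the patient via web conference, by phone or in person separate from the clinic visit".
- **Endpoint.** Within the acceptability endpoint, section 4.1 sets a listening target above 70% and defines the rate as "the proportion of patients in the intervention arm that log in to the online system and listen to (and how often) the recording". Section 17.1.2 repeats both.
- **Data source.** Section 6.4.1 (Audio & AVS Use) states: "Intervention use by patients will be monitored within the HealthPAL application". The application shows when the patient logs in, plays a recording and shares it. No field is described for who was operating the account.
- **Intended use.** Sections 5.2 and 6.1 describe patients reviewing the recording later, online at home. Section 5.1.1 asks them to listen within 24 hours, at one week, and within three days before the next visit.
- **Other uses of listening data.** Section 17.1.2 has staff contact patients who do not follow that regime. Section 10.2.1 samples Aim 2 patients by "recording use (listened to none, one or all recordings; shared recording or not".

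None of these sections removes training-session events, starts the count after training, sets a minimum play time or requires a demonstration account.

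**The concern.** A procedure planned for the whole AUDIO arm can itself produce the event that the endpoint counts. An RA who opens the patient's account and plays the recording may leave the same trace as a patient listening at home. The error runs in one direction: it can add listeners but cannot remove them.

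Listening is a component of the primary acceptability endpoint, and section 17.1.10 expects the pilot to inform whether a larger trial is feasible. A listening rate that partly measures delivery of training would overstate uptake of the intervention.

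There are two smaller effects. A play on the day of the visit can fill the 24-hour slot of the listening regime. It can also move a true non-listener out of the Aim 2 group that listened to none, if that group is drawn from the log. If the demonstration is repeated at interim recorded visits (section 5.1.2), the count of how often patients listen would be inflated too.

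**Working it through.** **The plan's own figures.** The 70% target is a chosen threshold with no derivation to reproduce. The sample-size arithmetic agrees with section 26.0: 3 × 30 = 90 patients, 3 × 6 = 18 clinicians, total 108.

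**Inputs**
- AUDIO patients: section 6.1 randomises in blocks of 2 within clinician, so about 90 / 2 = 45. Clinicians with an odd number of patients would move this slightly.
- Listeners needed: 0.70 × 45 = 31.5, so at least 32 (32 / 45 = 71.1%).
- h, the true share who listen outside the training session: not given for this trial, so assumed.
- f, the share of sessions that leave a login and a play in the patient's account, taken as unrelated to later listening: not given, so assumed.

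**Formulas**
- Logged rate p = h + (1 − h) × f.
- Chance of meeting the target = P(X ≥ 32), with X binomial (45, p).

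**Results at h = 50%**

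| f | Logged rate p | Chance of meeting target |
|---|---|---|
| 0 (clean count) | 0.50 | 0.3% |
| 0.25 | 0.50 + 0.50 × 0.25 = 0.625 | 14.9% |
| 0.50 | 0.50 + 0.50 × 0.50 = 0.75 | 78.4% |
| 0.80 | 0.50 + 0.50 × 0.80 = 0.90 | >99.9% |

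**Results at other values of h**
- h = 60%: 8.4% with a clean count, 50.9% at f = 0.25 and 94.8% at f = 0.50.
- h = 70%: 50.9% with a clean count, 88.4% at f = 0.25 and 99.5% at f = 0.50.
- h about 82%: about 98% with a clean count, so contamination has almost no room to change the result. This value comes from section 3.2.2, where 28 of 34 interviewed patients and caregivers (82%) reported listening. It is self-reported and comes from clinics that already shared recordings routinely.
- f = 1: the logged rate is 100% and the target is met whatever patients do afterwards.

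**Contamination needed to reach 70%.** Setting p = 0.70 gives f = (0.70 − h) / (1 − h). This is 0.20 / 0.50 = 0.40 at h = 50% and 0.10 / 0.40 = 0.25 at h = 60%. Well under all of the sessions would be enough.

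**Regime slots.** A day-0 play falls within the 24-hour slot of section 5.1.1. It cannot fill the one-week slot, and as a rule it cannot fill the slot before the next visit.

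**The case against.** - **A logged play is an inference.** The text says that playback is demonstrated under the patient's login. It does not say that a play is logged in every account, and for sessions held by phone an RA-run play is least certain. This stands, and it is why f is shown as a range.
- **The endpoint already means patient action.** It counts patients who log in and listen, and the log shows when events occur, so training events could be removed at analysis. This stands in part: the timing data should exist. But no rule says to use them, session end times are not stated to be recorded, and a filter chosen after the rates are seen would be a post hoc definition.
- **The non-adherence contact would still work.** A reader might infer that the trigger in section 17.1.2 would simply miss true non-listeners. The documents do not support that. A patient who never listens at home still fails the later regime slots, and section 6.3 adds a separate assessment of intervention use about one week after scheduled visits.
- **Aim 2 sampling may not use the log.** Section 10.2.1 does not name its source for recording use, so that effect is conditional.
- **The stakes are limited.** Sections 4.1 and 17.1.2 name recruitment of 108 participants as the primary indicator of acceptability. A missed target leads only to considering protocol changes. The instrumental-variable analysis in section 17.1.4 uses self-report. All of this stands and lowers the severity.
- **Some sources are not available here.** The HealthPAL manual, the HealthPAL instructions and the fidelity checklist (Appendices 4, 7 and 16) might cover the point. The endpoint definitions themselves do not.

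**Conclusion.** As written, the listening rate can be biased upward, because a session run by staff can leave the login and play that the endpoint counts and no rule removes it. This is likely for in-person sessions and less certain by phone.

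The size depends on two quantities that the documents do not give. If later listening is near 50%, contamination of half the sessions moves the chance of meeting the target from 0.3% to 78%. If it is near the 82% reported in other settings, the pass or fail result hardly changes, although the reported rate would still be too high.

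A reader might infer that every AUDIO patient will be logged as a listener, so that the target is met automatically. That would require a logged play in every session, which the text does not establish.

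This is a should-fix point with moderate confidence: a cheap improvement to one component of the acceptability endpoint, with no direct bearing on the randomised comparison of PAM-SF.

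**What to change.** In sections 4.1, 6.4.1 and 17.1.2, state that a patient counts as having listened only if HealthPAL records a play time-stamped after the end of the RA training session, and that events within any repeat session at an interim visit are also excluded. Have the RA record each session's end time on the existing fidelity checklist (section 17.3.2, Appendix 16). Alternatively, run the demonstration on a dummy account with a sample recording. Apply the same rule to the 24-hour slot of the listening regime and, where the log is used, to Aim 2 sampling.

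The cost is one time field and a filter on the log, or one demonstration account. The change should be made before data accrue, because without recorded end times staff-run and patient-run plays may not be separable later. The downside is small: the listening rate will look less favourable, and genuine listening during the session will not be counted.
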